Reaching and Engaging Depressed Senior Center Clients (REDS)

Principal Investigator: [name], Ph.D., Weill Cornell Medicine

IRB Protocol #: 1704018114

ClinicalTrials.gov Identifier: 03246789

Current Version: April 26, 2021

Prior Version Dates

July 16, 2018

July 15, 2019

June 9, 2020

BACKGROUND

Approximately 10,000 senior centers operate in the US and serve 1.25 million persons nationwide.¹ Most of their clients have low income,²⁻⁴ and in NYC, 68% are non-Caucasian.⁵ About 10% have clinically significant depression⁵ but most receive no care⁶. We developed SMART-MH,⁷ a community care model that can be embedded in senior centers to improve recognition of depression, referral, and adherence to depression treatment. We also developed Engage, a stepped-care therapy, streamlined based on the assumption that a dysfunction of the reward network is central to the pathogenesis of depression and using "reward exposure" as its principal intervention. Engage also targets negativity bias, apathy, and inadequate emotion regulation if they act as barriers to reward exposure.⁸ With our senior center partners and our mobile technology team, we redesigned Engage-M so that it can be used in a group format by licensed clinical social workers (LCSWs) of Senior Centers. Mobile technology provides probes for client adherence and offers to therapists easy to review summary records of mood, activity, and social interaction that can be used to target their sessions. We have integrated the SMART-MH model and Engage-M into a comprehensive community care model "Reaching and Engaging Depressed Senior Center Clients" (REDS). We will compare the performance of REDS with a comparison condition in four senior centers, two randomly assigned to REDS and two to a comparison condition. The comparison centers will use SMART-MH for recognition of depression and referral to mental health services plus weekly group meetings on "Wellness of Mind and Body" (W-MH). Our relationship with the NYC Dept. for Aging (DFTA) offers the opportunity to embed and rapidly deploy REDS in NYC Senior Centers, and may make the REDS model part of a sustainable service reimbursable by Medicare.

STUDY DESIGN

In response to the large numbers of senior center clients who suffer from untreated depression, we have partnered with the NYC Department for the Aging (DFTA) to develop SMART-MH, a community care model that can be embedded in senior centers to improve recognition, referral, and adherence to depression treatment. We also developed and tested Engage, a stepped-care therapy streamlined to use "reward exposure" as its principal intervention based on the assumption that dysfunction of the reward networks is central to the pathogenesis of depression. With our senior center partners and our mobile technology team, we redesigned Engage-M so that it can be used in a group format by licensed clinical social workers (LCSWs) of Senior Centers. Mobile technology provides probes for client adherence and offers to therapists easy to review summary records of mood, activity, and social interaction that can be used to target their sessions. We have integrated SMART-MH and Engage-M into a comprehensive community care model "Reaching and Engaging Depressed Senior Center Clients" (REDS). The specific aims of this developmental project are to: 1. Finalize the REDS protocol and assess feasibility of training; 2. Prepare an Operations' Manual; 3. Examine reach, feasibility, and acceptability of REDS; 4. Examine engagement of behavioral targets and preliminary effectiveness; and 5) Collect information on REDS cost, barriers to implementation, and potential savings in health care utilization. We will randomly assign four senior centers to offer either Engage-M (N=40), the treatment offered by REDS (1 individual and 8 weekly group sessions) or 8 group sessions "Wellness in Mind and Body" plus mental health referral (W-MH; N=20). The participants will have clinically significant depressive symptoms (PHQ-9 \geq 10) and will be older and middle-aged adults (55+); 12.6% of the NYC senior center clients are aged 55-65 years. Clients will be identified by senior center staff trained in SMART-MH strategies. We will offer additional training to staff of all centers on SMART-MH outreach, depression screening, and treatment engagement. We will train and provide weekly supervision to 2 or more LCSWs per center of the two centers assigned to Engage-M. We will not offer training or supervision to senior center staff leading the groups of W-MH but we will provide oversight so that clients receive mental health referrals and are

encouraged to attend weekly Wellness group meetings. Our findings will set be used in a R01 study to formally test the feasibility, acceptability, effectiveness, non-billable costs, and barriers of REDS beyond NYC. If proven effective, with administrative support, REDS can be extended nationally and supported by billable services.

We will continue to work with senior centers' staff and our mobile technology team to finalize REDS for both English and Spanish-speaking participants. We will record the training hours to achieve certification in Engage-M (part of REDS), and the success rate of LCSWs engaged by the senior centers to offer behavioral services.

Across conditions we will evaluate: 1) Reach: Number of clients screened with PHQ-9 score greater than or equal to 10 vs. all eligible for screening, and those who receive REDS or W-MH; 2) Feasibility: Number of clients who initiate therapy and research procedures (sessions attended, smartphone use); 3) Acceptability to clients [Client Satisfaction Questionnaire 10,11 (CSQ), session completion rate] at baseline, 6, 9, and 12 weeks. Satisfaction of LCSWs, center staff will be assessed every 6 months throughout the study. Benchmarks: Feasibility: >80% will participate in each session of Engage-M. Acceptability: Engage-M participants will have a mean CSQ score ≥ 3 (out of 4) at the end of treatment. 70% of Engage-M clients will enter their smartphone ratings in more than 70% of study days (59 out of the 85 days).

We will be recruiting 60 subjects in total from all sites (WCMC only site) and six licensed clinical social worker subjects. 1. Recruitment and referral sources: We are working with [name] and [name] of the NYC Department for the Aging (DFTA) to plan implementation of the REDS project at 4 NYC senior centers. Older and middle-aged (55+) senior center clients with elevated depressive symptoms (LCSW training phase n=10 clients; Effectiveness Pilot n=60) will be recruited from the 4 participating senior centers. Clients in the startup phase, during which LCSWs are trained, will be recruited from each of 2 centers randomly assigned to REDS (n=10) over a 4-month period. For the RCT, 20 clients will be recruited from each of 2 centers randomly assigned to REDS (n=40), and 10 from each of 2 centers assigned to the Wellness groups plus mental health referral (W-MH; n=20) over approximately a 14-month period. We have chosen to partner with senior centers that represent clients from diverse backgrounds. Each partnering senior center documents at least 800 active members each, with a daily participation rate of at least 200 members. Given an expected 10% rate of eligible clients (PHQ-9 > 10), we expect at least 80 clients at each center to meet inclusion criteria to be referred to the study. Excluding those with severe mental illness or dementia as assessed via research measures, we anticipate that over 60 clients at each center will meet inclusion criteria for the RCT. This study will recruit from four senior centers overseen and funded by the Department for the Aging in New York City. We estimate that our sample will be similar to the sample of the demographic profile of NYC senior center members indicate a mean age of 76 year; 67% women; 32% White, 26% Hispanic, 23% Asian, 17% African-American, and 2% other. Support services to investigators and projects will be organized by the Research Methods Core (RMC) Data Group, directed by [name] assisted by two data managers: [name], MPH, and [name], MS, MPH. The Team will meet weekly to: 1) review the pace and quality of data entering; 2) determine priorities; and 3) provide consultation and conduct analyses. Investigators will join the Work Group as needed to inform the Group of their progress and needs and to be directed to offer their specialized expertise to other Center supported studies. We have used this model successfully over 20 years in our NIMH supported Center. Instrument Sharing: The Intervention Management Work Group (IMG) of the Administrative Core consults with investigators using Center resources to ensure that they select from measurement instruments used in the Center's ongoing studies so that results can be compared across studies. Data Collection Forms: In addition to

harmonizing the selection of instruments across studies, investigators will also be encouraged to use data elements (e.g. demographic definitions and variable names) that have been used on previous studies. This again will harmonize the study data to allow easier merging of data across studies for hypothesis generation and exploratory analyses for future studies. Prototype Database: We have developed a relational database system and a tracking system in Microsoft Access that serve as the prototype for implementing each Center study database. Our database system ensures that the procedures are standardized and administered as intended by the design and that the collection of other data elements is standardized. The tracking system monitors patient appointments and assessments and produces reports of missing and delinquent data. Data from Community Agencies: We have worked with community agencies to facilitate the transfer of de-identified data to Weill Cornell. Each agency compiles patient data from its databases (e.g., CMS OASIS, Medication, Service Utilization) according to our specifications and removes identifying information.

INCLUSION AND EXCLUSION CRITERIA

Client Inclusion Criteria Referral to study (stage 1): 1. Age at least 55 years. 2. PHQ-9 score of 10 or higher via routine screening by senior center staff 3. English or Spanish speaking. Research assessment (stage 2): 1. MOCA greater than or equal to 24. 2. Capacity to provide written consent for both research assessment and the Engage-M intervention.

Client Exclusion Criteria 1. Current active suicidal ideation defined by MADRS Suicide Item 10 greater than or equal to 4 (Probably better off dead. Suicidal thoughts are common, and suicide is considered as a possible solution, but without specific plans or intention). 2. Presence of psychiatric diagnoses other than unipolar, non-psychotic major depression or generalized anxiety disorder by SCID-V. 3. Severe or life-threatening medical illness (e.g., end stage organ failure).

DATA AND SAFETY MONITORING PLAN

We will monitor depressive symptoms and functioning for each participant via clinical research assessments throughout the study period. Feedback will be collected from participants on their use of the data collection app. In addition, a DSMB board assembled for the entire ALACRITY Center NIMH grant (1 P50 MH113838-01, PI: [name]) will review the study design, IRB protocol, adverse events, and interim reports of the ongoing study.

If investigators note increasing rates of adverse events or suicidal ideation, we would stop the study. We do not anticipate this will be the case.

Some participants may find the daily questions of the HR application boring or tedious, or they may be bothered by the phone battery usage required to keep the app running, and may choose to discontinue using the application or withdraw from the study. Participants may become seriously medically ill and decide not to participate. In addition, if new psychiatric symptoms develop or change in severity, we may recommend removal from the study and provide referrals for the appropriate treatment needed. Referrals will include psychotherapy or medication management referrals in the community.

Cornell research staff will also assess changes in depressive symptoms at regular intervals. Patient's health and clinical care will always take priority over study participation. Participants may not want to continue completing daily questions via the HR app and will be free to discontinue usage at any time. Participants will also have the option to disable cellular data use for the app through their device settings.

Study interviewers will be Weill Cornell research staff who are trained in assessments with older adults. They will specifically inquire about depressive symptoms, falls, and hospitalizations. Study therapists are also trained to monitor the participant's mental state and will report symptom severity to Weill Cornell staff and the principal investigator. If any moderate to severe symptom changes (or new symptoms) are noted, we will consider alternative options to maximize the participant's well-being. In addition, we will ask all participants about the burden of active and passive sensing and daily smartphone usage, to identify any potential negative consequences of using the HR app. We do not expect any additional risk of adverse events by adding active and passive sensing data collection.

Referrals to external mental health agencies will be offered to participants who drop out of the study in order to address any ongoing depressive symptoms. For those subjects who are removed from the study due to active suicidal ideation or clinically worsening symptoms of depression referrals will be provided for the appropriate treatment needed. Referrals will include psychotherapy or medication management referrals in the community.

The study will adhere to the adverse event grading guidelines provided by Weill Cornell's Office of Research Integrity and Assurance. All adverse events will be reported to the Weill Cornell IRB in the timeline indicated by the Weill Cornell Human Research Protection Program Immediate Reporting Policy.

We will periodically report adverse events to the DSMB, in addition to reporting to the IRB as per Weill Cornell's policy.

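### Is the Engage-M attendance benchmark too ambiguous, or its 80% floor too strict, to stand as written?

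*Protocol*

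**What the plan says.** All the relevant text is in the Study Design section of the Protocol.

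- The treatment is "Engage-M (N=40), the treatment offered by REDS (1 individual and 8 weekly group sessions", which makes nine sessions for 40 clients. The recruitment paragraph agrees: "20 clients will be recruited from each of 2 centers randomly assigned to REDS (n=40".
- The feasibility measure is "Feasibility: Number of clients who initiate therapy and research procedures (sessions attended, smartphone use". The session completion rate appears separately, under acceptability: "Acceptability to clients [Client Satisfaction Questionnaire 10,11 (CSQ), session completion rate] at baseline, 6, 9, and 12 weeks".
- The attendance benchmark is "Benchmarks: Feasibility: >80% will participate in each session of Engage-M". It gives no denominator, expected attendance or probability of success.
- The smartphone benchmark, two sentences later, specifies both the share of clients and the share of days: "70% of Engage-M clients will enter their smartphone ratings in more than 70% of study days".
- On use of the results, the section says: "Our findings will set be used in a R01 study to formally test the feasibility". It attaches no go/no-go rule to the benchmark.

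**The concern.** The benchmark sentence has no explicit subject, so a reader can ask what the 80% is a percentage of. Reading A takes the session as the unit: more than 80% of clients are present at every session. Reading B takes the client as the unit: more than 80% of clients attend all nine. The smartphone benchmark is written per client, which lends B some support. If the choice were open, it could be made after attendance was known, and a statement that the benchmark was met would have no fixed meaning.

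The second worry is that reading A is harder to meet than its 80% label suggests, because nine sessions must all clear the floor. A programme with 85% true attendance could well be reported as missing an 80% target. Feasibility belongs to the third aim and the results feed a later grant, so a misleading verdict would matter somewhat.

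**Working it through.** **Inputs.** Clients: 40. Sessions: 1 + 8 = 9. Threshold: more than 0.80 × 40 = 32, so at least 33. The Protocol gives neither true attendance p nor within-client correlation, so both are assumptions and are varied below. It derives no figure for this benchmark, so there is nothing to reproduce.

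**Can the readings disagree?** Yes. Let each of the 40 clients miss exactly one session, spread evenly. Since 40 = 4 × 9 + 4, four sessions have 35 present and five have 36 (87.5% or 90%). A is met. Nobody attends all nine, so B is missed.

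**Must they disagree?** No. B implies A, because 33 clients who attend everything put at least 33 in each session. If absence is permanent dropout, the number present at session 9 equals the number who attended all nine, so A and B give the same answer.

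**Chance of meeting each reading, independent attendance.**

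- A: P(X ≥ 33 | 40, p)^9. At p = 0.85, 0.7559^9 = 0.081. At p = 0.90, 0.9581^9 = 0.680.
- B: P(X ≥ 33 | 40, p^9). At p = 0.90, p^9 = 0.387, so about 15.5 of 40 are expected to attend all nine.

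| True attendance | A | B |
|---|---|---|
| 80% | 0.06% | 0% |
| 85% | 8.1% | 0% |
| 88% | 38.9% | 0% |
| 90% | 68.0% | 0% |
| 92% | 89.1% | 0% |
| 95% | 99.4% | 0.6% |

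Under independence A has an even chance at 88.8% attendance and an 80% chance at 91.0%. For B the figures are 97.7% and 98.3%.

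**With within-client correlation** (beta-binomial simulation, constant attendance of 90%). Because B implies A, the chance of disagreement is A minus B.

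| Correlation | A | B | Disagree |
|---|---|---|---|
| 0.2 | 73.1% | 0.2% | 72.9% |
| 0.4 | 78.2% | 6.4% | 71.8% |
| 0.6 | 83.4% | 34.6% | 48.8% |
| 0.8 | 88.6% | 74.3% | 14.3% |

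The even-chance point for A falls from 88.8% under independence to about 88% (correlation 0.2), 87% (0.4), 86% (0.6) and just under 85% (0.8). A bar near 90% therefore describes an 80% chance of success, or the independence case. It is not a fixed property of the benchmark.

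**Is strictness peculiar to this rule?** Only in degree. One session alone, at 33 of 40, has an 81.1% chance of passing at p = 0.86, so any observed cut needs true attendance above the cut to pass reliably. The per-session form also gains something. If attendance falls linearly from 95% to 70% over the nine sessions (mean 82.5%), A passes 0.02% of the time, while a rule on mean attendance above 80% passes 89%. The floor detects late drop-off that the average hides.

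**Denominator.** Thirty-two present is 32/36 = 88.9% if 36 clients start, but 32/40 = 80.0% of all 40, which is not above 80%. The choice can matter at the margin.

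**The case for a change.** The strongest case for a change is that the Protocol fixes a numeric criterion itself, so its unit and denominator should be fixed with it. The cost would be a sentence or two. Reading B is not contrived, the two readings can part on real attendance sheets, and even a reader who accepts A cannot tell whether the base is 40 or those who start. Feasibility is a stated aim, and this is the only benchmark labelled as such.

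Part of this stands. The denominator is not named, and the example with 32 present shows that it could tip a borderline session. B is a possible reading, though a less natural one.

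The rest is weaker. Setting the target for each session makes the session the unit. The smartphone benchmark shows that its authors wrote a client-by-threshold rule when they wanted one. Its attendance analogue would be a share of clients attending more than some share of sessions, not all nine. The charge of hidden strictness needs a claimed pass probability to contradict, and there is none. The choice between all 40 and those who start, like supplementary attendance summaries, is commonly settled in a statistical analysis plan, which may exist but is not at hand.

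**Conclusion.** No change to the plan is needed. Followed as worded, the benchmark is a floor at every session, at least 33 of 40 if all enrolled Engage-M clients are counted, and that gives a sound descriptive result. Its even-chance point lies at about 85% to 89% true attendance. This assumes constant attendance, 40 as denominator, nine sessions and within-client correlation from 0.8 down to 0. It reflects a strict floor and is not an error. The possible conflict with the all-nine reading is large when absences are scattered (about 72% at 90% attendance and correlation 0.4), small when they cluster in the same clients (about 14% at correlation 0.8) and absent under pure dropout.

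What remains is an unnamed denominator in a developmental pilot with no decision tied to the result. Sessions attended and session completion are already collected. An analyst can report counts per session against both 40 and the number who start, so readers can judge attendance without relying on the met-or-not-met label.

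### The smartphone benchmark asks for more than 70% of study days but glosses this as 59 of 85, which is 69.4%; with 85 days the minimum is 60

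*Protocol*

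**What the plan says.** The benchmarks close the Study Design paragraphs on reach, feasibility and acceptability, which correspond to aim 3. The smartphone benchmark reads "70% of Engage-M clients will enter their smartphone ratings in more than 70% of study days (59 out of the 85 days"). It has two layers: a per-client rule (the share of days on which that client enters ratings) and a group target (the share of Engage-M clients who meet the rule). The point here concerns only the per-client rule, which is given once as a percentage and once as a count of days.

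No other part of the protocol states a number of study days or another cut-off. The nearest context is the schedule for client satisfaction, "at baseline, 6, 9, and 12 weeks". The natural denominator for the group target is the 40 Engage-M clients, stated in Study Design ("We will randomly assign four senior centers to offer either Engage-M (N=40") and again in the recruitment paragraph ("20 clients will be recruited from each of 2 centers randomly assigned to REDS (n=40").

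**The concern.** The percentage is a strict inequality, and the count in the parenthesis falls just below it. The sentence therefore allows two cut-offs:

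- 59 as the qualifying count, which is the more natural reading. A client with exactly 59 days then passes, although the percentage rule excludes that client.
- 59 as a truncated 70% mark that must be exceeded. The minimum is then 60 and the two statements agree, but the text does not say this.

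At stake is how a boundary client is scored on a stated benchmark. If the cut-off is left open until the data are in, whoever scores the benchmark can choose between 59 and 60 after seeing which helps. The protocol intends its findings to feed a later R01 study, so the benchmark should be scored one way only. Sample size, error rates, eligibility and safety rules are not touched.

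**Working it through.** **Inputs, all from Study Design:** the per-client rule is strictly above 70% of study days; the printed count is 59; the printed denominator is 85; there are 40 Engage-M clients.

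**Trying to reproduce the printed count.** The rule needs the smallest whole number k with k/85 > 0.70.

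- 0.70 × 85 = 59.5
- 59/85 = 0.6941, or 69.4%, which is 0.6 points below 70%: fails
- 60/85 = 0.7059, or 70.6%, which is 0.6 points above 70%: passes

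So k = 60, and 59 is not reproduced. Dropping the decimal from 59.5 gives 59, but a count truncated below a strict threshold cannot satisfy that threshold. Rounding up, or to the nearest day with halves up, gives 60.

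**Does another denominator explain 59?** The smallest count above 70%, for nearby numbers of days:

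| Study days | 70% of days | Smallest qualifying count | As a percentage |
|---|---|---|---|
| 83 | 58.1 | 59 | 71.1% |
| 84 | 58.8 | 59 | 70.2% |
| 85 (printed) | 59.5 | 60 | 70.6% |
| 86 | 60.2 | 61 | 70.9% |

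Of all denominators from 70 to 99 days, only 83 and 84 make 59 the minimum. Twelve weeks is 12 × 7 = 84 days; counting the baseline day as well gives 85.

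**Effect on the benchmark.** With 40 clients, the 70% group target is 0.70 × 40 = 28 clients, and each client at exactly 59 days moves the observed rate by 1/40 = 2.5 points. A single boundary client could decide between 27 and 28.

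**How many clients might sit at exactly 59 days?** The protocol gives no basis for this, so every row below is an assumption. The expected number is 40 × P(count = 59).

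| Assumption about day counts | Expected clients of 40 | Shift in observed rate (points) |
|---|---|---|
| Evenly spread over 0 to 85 (40/86) | 0.5 | 1.2 |
| Binomial(85, 0.60), same probability for all clients | 0.7 | 1.8 |
| Binomial(85, 0.70) | 3.7 | 9.3 |
| Binomial(85, 0.75) | 1.9 | 4.8 |
| Binomial(85, 0.80) | 0.3 | 0.6 |
| Binomial(85, 0.90) | under 0.001 | none |
| Beta-binomial, mean 0.70, intraclass correlation 0.1 | 1.1 | 2.8 |
| Beta-binomial, mean 0.70, intraclass correlation 0.3 | 0.5 | 1.3 |

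The binomial case at 0.70 is close to the worst possible, because it puts every client's expected count (59.5) on the cut-off. Once clients are allowed to differ in adherence, as in the beta-binomial rows, the peak largely disappears.

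**The case against.** The arithmetic is not in dispute; the case on the other side concerns weight and remedy.

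*The percentage governs.* It stands in the same sentence and is unambiguous, so an analyst who applies it arrives at 60 without any amendment. The 59 is only a gloss, probably 59.5 with the decimal dropped. This is fair, and it is why the point is small. But the gloss is the only count printed, and it contradicts the rule beside it.

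*The cut-off belongs in the SAP.* An SAP, which is not available here, could fix the operational rule. That would not make the printed count correct, and an SAP that copied the sentence would carry the conflict forward. The problem is a wrong figure, not missing detail.

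*The 9.3-point scenario is unrealistic.* This stands. It requires all 40 clients to share one daily entry probability of 0.70 with independent days. Roughly one client or fewer is the fairer expectation, and the larger figure should not set the importance of the point.

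*The slip may lie in the 85.* The last client assessment is at 12 weeks, or 84 days, and 59 is exactly the smallest count above 70% of 84. This stands as a possibility. However, 85 is the only denominator printed, it fits 12 weeks with the baseline day counted, and nothing else in the protocol gives 84 as the rating window. If 84 was meant, the sentence still needs correcting, in its other figure.

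**Conclusion.** The concern holds. With 85 study days, as printed, 59 days does not meet the rule of more than 70%; the minimum is 60. That conclusion rests only on the three figures in the sentence.

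The consequence is minor: a one-day difference, confined to clients at exactly 59 days, in a benchmark with no decision attached. The 2.5 points per affected client assume that all 40 Engage-M clients form the denominator. The expected number of affected clients depends wholly on assumptions about adherence and is likely to be about one or fewer, unless adherence clusters tightly around 70%. The correction should be made, but nothing else in the design depends on it.

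**What to change.** Replace the parenthesis with: at least 60 of the 85 days. If the sponsor confirms that ratings are collected over 84 days, write instead: at least 59 of the 84 days (70.2%). Either way, percentage, count and denominator should agree before the benchmark is scored.

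The cost is one corrected figure. Compared with reading 59 as the minimum, the benchmark becomes harder by one day; compared with reading it as more than 59, nothing changes.
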